4.2 METHOD OF TREATMENT ASSIGNMENT

Since this is an open-label study, the Sponsor and its agents, the study site personnel, and the patients' parents/caregivers will be aware of the treatment administered in this study.

All patients will receive the same open-label treatment with the dose determined by both body weight and age (see Section 3.3.1), thus a method for assigning treatment is not warranted.

4.3 STUDY TREATMENT AND OTHER TREATMENTS RELEVANT TO THE STUDY DESIGN

The investigational medicinal product (IMP) for this study is baloxavir marboxil.

4.3.1 Study Treatment Formulation, Packaging, and Handling

Baloxavir marboxil will be supplied by the Sponsor as white to light yellow granules for oral suspension in 50-mL glass bottles. For information on the formulation and handling of baloxavir marboxil, see the pharmacy manual.

4.3.2 Study Treatment Dosage, Administration, and Compliance

The treatment regimens are summarized in Section 3.1.

4.3.2.1 Baloxavir Marboxil

Baloxavir marboxil is provided as granules for oral suspension; it will be administered orally as a single dose on Day 1, only. The granules for oral suspension will be reconstituted with water to provide a fixed dose depending on both the body weight and age of the child (2 mg/kg ≥ 3 months, 1 mg/kg < 3 months).

4.3.2.2 Overdose or Incorrect Administration

Any dose modification should be noted on the Study Drug Administration electronic Case Report Form (eCRF). Cases of overdose, medication error, drug abuse, or drug misuse, along with any associated adverse events, should be reported as described in Section 5.3.5.11.

4.3.3 Rescue Medication

If influenza symptoms, such as fever and headache, are so severe, in the opinion of the patient/caregiver, that the patient needs rescue therapy between Day 1 and Day 29, the use of acetaminophen at a dose appropriate to the body weight and age of the child will be permitted only for the relief of fever or pain. If acetaminophen is used, the parent/caregiver will record the use in the patient diary, and the investigator will record the date, time, and dose at the next visit. Acetaminophen will not be provided by the Sponsor.

4.3.4 Investigational Medicinal Product Accountability

The IMP required for completion of this study (baloxavir marboxil) will be provided by the Sponsor where required by local health authority regulations. The study site will acknowledge receipt of the IMP supplied by the Sponsor, using the interactive voice or web-based response system (IxRS) to confirm the shipment condition and content. Any damaged shipments will be replaced.

The IMP will either be disposed of at the study site according to the study site's institutional standard operating procedure or be returned to the Sponsor (if supplied by the Sponsor) with the appropriate documentation. The site's method of destroying Sponsor-supplied IMP must be agreed to by the Sponsor. The site must obtain written

authorization from the Sponsor before any Sponsor-supplied IMP is destroyed, and IMP destruction must be documented on the appropriate form.

Accurate records of all IMP received at, dispensed from, returned to, and disposed of by the study site should be recorded on the Drug Inventory Log.

4.3.5 Continued Access to Baloxavir Marboxil

Currently, the Sponsor does not have any plans to provide the Roche IMP (baloxavir marboxil) or any other study treatments or interventions to patients who have completed the study. The Sponsor may evaluate whether to continue providing baloxavir marboxil in accordance with the Roche Global Policy on Continued Access to Investigational Medicinal Product, available at the following web site:

http://www.roche.com/policy_continued_access_to_investigational_medicines.pdf

4.4 CONCOMITANT THERAPY

Concomitant therapy consists of any medication (e.g., prescription drugs, over-the-counter drugs, vaccines, herbal or homeopathic remedies, nutritional supplements) used by a patient in addition to protocol-mandated treatment from 2 weeks prior to the initiation of study drug, to the study completion/discontinuation visit. All such medications should be reported to the investigator and recorded on the Concomitant Medications eCRF.

4.4.1 Permitted Therapy

Acetaminophen is permitted between Day 1 and Day 29 for severe influenza symptoms at a dose appropriate to the body weight and age of the child. See Section 4.3.3 for further details.

4.4.2 Cautionary Therapy

4.4.2.1 Herbal Therapies

Concomitant use of herbal therapies during this study is not recommended because their pharmacokinetics, safety profiles, and potential drug–drug interactions are generally unknown.

4.4.2.2 Polyvalent Cation–Containing Products

Polyvalent cation–containing products may decrease plasma concentrations of baloxavir. Thus, polyvalent cation-containing oral laxatives or oral antacids and oral supplements containing iron, zinc, selenium, calcium, or magnesium should not be taken with baloxavir marboxil.

4.4.3 Prohibited Therapy

The use of the following drugs and over-the-counter drugs with equivalent efficacy are prohibited from Day 1, after administration of study drug, until study completion or early termination:

- Systemic antiviral drugs
- Antipyretics/analgesics except acetaminophen
- Corticosteroids in injection, oral, or inhalation formulation
- Immunosuppressants

4.5 STUDY ASSESSMENTS

The schedule of activities to be performed during the study is provided in [Appendix 1](#). All activities should be performed and documented for each patient.

Patients will be closely monitored for safety throughout the study.

4.5.1 Informed Consent Forms and Screening Log

Potential patients will be prescreened using an influenza test (RIDT or PCR) and a COVID-19 test (*RAT or PCR*). This is to ensure that patients with a high probability of having influenza infection are enrolled and to minimize the likelihood of enrolling a patient with COVID-19 in the study. A separate informed consent procedure will be implemented for this prescreening step. *If sites perform influenza (RIDT or PCR) and/or COVID-19 tests (RAT or PCR) as part of standard of care assessment, test results recorded in the patient medical record can be used for eligibility assessment, if samples were collected within 48 hours of screening.*

Written informed consent for participation in the study must be obtained from the child's parent/caregiver or legal guardian before performing any study-related procedures (including screening evaluations).

Informed Consent Forms for enrolled patients and for patients who are not subsequently enrolled will be maintained at the study site.

All screening evaluations must be completed and reviewed to confirm that patients meet all eligibility criteria before enrollment. The investigator will maintain a screening log to record details of all patients screened and to confirm eligibility or record reasons for screening failure, as applicable.

4.5.2 Medical History, Concomitant Medication, and Demographic Data

Medical history, including clinically significant diseases, surgeries, and cancer history (including prior cancer therapies and procedures), will be recorded at baseline. In addition, all medications (e.g., prescription drugs, over-the-counter drugs, vaccines, herbal or homeopathic remedies, nutritional supplements) used by the patient within

2 weeks prior to initiation of study treatment will be recorded. At the time of each follow-up physical examination, an interval medical history should be obtained and any changes in medications and allergies should be recorded.

Demographic data will include age, sex, and parent/caregiver-reported race/ethnicity.

Influenza vaccination history for the 12 months before screening will be recorded, including the type of vaccine (e.g., live, inactivated) and date administered, if known.

4.5.3 Physical Examinations

A complete physical examination, performed at screening and other specified visits, should include an evaluation of the head, eyes, ears, nose, and throat, and the cardiovascular, dermatologic, musculoskeletal, respiratory, gastrointestinal, genitourinary, and neurologic systems. Any abnormality identified at baseline should be recorded on the General Medical History and Baseline Conditions eCRF.

Limited, symptom-directed physical examinations should be performed at specified post-baseline visits and as clinically indicated. Changes from baseline abnormalities should be recorded in patient notes. New or worsened clinically significant abnormalities should be recorded as adverse events on the Adverse Event eCRF.

Limited, symptom-directed physical examinations may be performed by a mobile nursing professional.

4.5.4 Vital Signs

Vital signs will include measurements of respiratory rate, pulse rate, and systolic and diastolic blood pressure as well as tympanic temperature.

Temperature will also be measured and recorded by parents/caregivers in patients eDiary (Section 4.5.6).

4.5.5 Laboratory and Other Biological Samples

Samples for the following laboratory tests will be sent to one or several central laboratories for analysis:

- Hematology: WBC count, RBC count, hemoglobin, hematocrit, platelet count, differential count (neutrophils, eosinophils, basophils, monocytes, lymphocytes, other cells)
- Chemistry panel (serum or plasma): sodium, potassium, chloride, bicarbonate, BUN or urea, creatinine, total protein, albumin, total and direct bilirubin, alkaline phosphatase, ALT, AST
- Plasma samples for PK analysis

- Nasopharyngeal swabs for virology tests (i.e., reverse transcriptase-polymerase chain reaction [RT-PCR], TCID₅₀, viral phenotyping and genotyping) and for non-influenza respiratory pathogen coinfections panel (only at the screening visit)

For sampling procedures, storage conditions, and shipment instructions, see the laboratory manual.

Biological samples will be destroyed when the final Clinical Study Report has been completed, with the following exception:

- Plasma samples collected for PK analysis may be needed for PK assay development and validation; therefore, these samples will be destroyed no later than 5 years after the final Clinical Study Report has been completed.

When a patient withdraws from the study, samples collected prior to the date of withdrawal may still be analyzed, unless the patient specifically requests that the samples be destroyed or local laws require destruction of the samples. However, if samples have been tested prior to withdrawal, results from those tests will remain as part of the overall research data.

Data arising from sample analysis will be subject to the confidentiality standards described in Section 8.4.

4.5.6 Patient-Reported and Investigator-Reported Outcomes

The Canadian Acute Respiratory Illness and Flu Scale (CARIFS) will be used to document the treatment benefit of baloxavir marboxil.

CARIFS is a reliable parental questionnaire and is composed of 18 questions, each with a 4-point Likert response. The questionnaire covers three domains: symptoms (e.g., cough), function (e.g., play), and parental impact (e.g., clinginess). The CARIFS is calculated as the sum of the items and measures duration of illness. Data handling conventions will be defined and described in the statistical analysis plan.

The questionnaire will be completed in its entirety by the parent or caregiver at specified time points during the study (see [Appendix 1](#)). To ensure instrument validity and that data standards meet health authority requirements, the questionnaire will be self-administered before the parent or caregiver receives any information on disease status, prior to the performance of non-patient-reported outcome (PRO) assessments, and prior to the administration of study treatment, unless otherwise specified (see [Appendix 1](#)).

Parent/caregivers will use an electronic device to capture PRO data. The electronic device and/or instructions for completing the questionnaires electronically will be provided by site staff. The data will be transmitted to a centralized database maintained by the electronic device vendor. The data will be available for access by appropriate study personnel.

In addition, a 4-question palatability assessment (performed by the investigator or delegate) will be used to determine the perceived acceptability of baloxavir marboxil for each patient and issues that occur with regard to dosing (see [Appendix 4](#)).

Palatability plays a role in patient acceptability of a drug especially in the pediatric population and is likely to have a significant impact on a patient's adherence, especially when the medicinal product has to be given as multiple doses either daily or over a number of days. This is largely determined by the characteristics of the medicinal product and the user, and compliance rates in children can range widely with factors attributed to formulation and palatability. There will be no formal statistical analysis performed for this endpoint.

Parent or Caregiver Reported Temperature

The parents or caregivers will measure the patient's temperature using tympanic thermometers provided. The temperature will be measured at specific time points during the study and will be recorded in the patient's electronic diary ([Appendix 1](#))

The electronic device and/or instructions for recording the temperature electronically will be provided by site staff. The data will be transmitted to a centralized database maintained by the electronic device vendor. The data will be available for access by appropriate study personnel.

4.6 TREATMENT, PATIENT, STUDY, AND SITE DISCONTINUATION

4.6.1 Study Treatment Discontinuation

Patients must permanently discontinue study treatment if they experience any of the following:

- Any medical condition that the investigator or Sponsor determines may jeopardize the patient's safety if he or she continues to receive study treatment
- Investigator or Sponsor determination that treatment discontinuation is in the best interest of the patient

The primary reason for study treatment discontinuation should be documented on the appropriate eCRF. Patients who discontinue study treatment prematurely will not be replaced.

Patients will return to the clinic for a treatment completion or treatment discontinuation visit on Day 29 (± 3) days (see [Appendix 1](#) for additional details).

4.6.2 Patient Discontinuation from Study

Patients' parents/caregivers have the right to voluntarily withdraw the patient from the study at any time for any reason. In addition, the investigator has the right to withdraw a patient from the study at any time. Reasons for withdrawal from the study may include, but are not limited to, the following:

- Patient's parent/caregiver withdrawal of consent

- Study termination or site closure
- Patient's parent/caregiver non-compliance, defined as failure to comply with protocol requirements as determined by the investigator or Sponsor

Every effort should be made to obtain information on each patient who was withdrawn from the study by the parent/caregiver. The primary reason for withdrawal from the study should be documented on the appropriate eCRF. If a parent/caregiver requests that the patient be withdrawn from the study, this request must be documented in the source documents and signed by the investigator. Patients who are withdrawn from the study will not be replaced.

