5.1.2 Management of Patients Who Experience Adverse Events

Baloxavir marboxil is administered as a single-dose treatment, so no dose modification or treatment discontinuation is possible.

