5.3.1 Adverse Event Reporting Period

Investigators will seek information on adverse events at each patient contact. All adverse events, whether reported by the parent/caregiver or noted by study personnel, will be recorded in the patient's medical record and on the Adverse Event eCRF.

After informed consent has been obtained but prior to initiation of study drug, only serious adverse events caused by a protocol-mandated intervention (e.g., invasive procedures such as biopsies, discontinuation of medications) should be reported (see Section 5.4.2 for instructions for reporting serious adverse events).

After initiation of study drug, all adverse events will be reported until 28-days after the last dose of study drug.

Instructions for reporting adverse events that occur after the adverse event reporting period are provided in Section 5.6.

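### Protocol 4.6.2 allows a dosed infant to be withdrawn for caregiver non-compliance, and nothing ensures that new adverse events are sought to Day 29 afterwards

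*Protocol*

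**What the plan says.** Protocol 4.6.2 states that "the investigator has the right to withdraw a patient from the study at any time". It introduces its list with "Reasons for withdrawal from the study may include, but are not limited to, the following", and one listed reason is "Patient's parent/caregiver non-compliance, defined as failure to comply with protocol requirements as determined by the investigator or Sponsor". It adds that "Patients who are withdrawn from the study will not be replaced". Its only instruction on recovering data is "Every effort should be made to obtain information on each patient who was withdrawn from the study by the parent/caregiver".

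Protocol 5.1.2 states: "Baloxavir marboxil is administered as a single-dose treatment, so no dose modification or treatment discontinuation is possible". Protocol 5.3.1 requires that after study drug initiation "all adverse events will be reported until 28-days after the last dose of study drug", and says that investigators ask about adverse events at each patient contact. Protocol 3.1 makes the visits on Days 2, 4, 6, 10 and 29 mandatory.

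Protocol 6.1.6 and SAP 3 (Safety Set) keep every infant who received any part of the dose in the safety population, with or without follow-up visits. SAP 4.2.1.1 summarises adverse events by onset on Days 1–7, Days 8–14 and Day 15 or later. SAP 1.2.3 says that the primary analysis will include safety follow-up data from patients who withdrew before Day 29. SAP 4.1 (Visit Windows) limits summaries of adverse events and concomitant medications to data up to the date of study completion or discontinuation.

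**The concern.** In a trial with continuing treatment, withdrawal for non-compliance can at least stop exposure. Here exposure is complete on Day 1, and all that remains to stop is data collection for the primary objective, which is safety. The rule sets no threshold for non-compliance, and the caregiver's task is demanding: four temperatures a day on Days 1 to 3, and the symptom questionnaire twice a day to Day 9.

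Because the denominator is everyone dosed, incomplete follow-up does not show in the headline percentage. An infant withdrawn on Day 5 who has an event on Day 12 is reported as a dosed infant without that event. The error in incidence can only go downward, and it falls mainly on the Day 8–14 and Day 15-or-later windows. Withdrawal before Day 6 would also lose the Visit 4 laboratory draw, the only follow-up draw that is not conditional, which feeds the liver criteria in SAP Table 3.

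Efficacy is affected less directly. SAP 4.3.1 censors withdrawn patients at their last observation. If non-compliance is related to how ill the infant is, that censoring is informative. Such a link is plausible, but the documents neither show nor exclude it.

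**Working it through.** **Does any passage already keep the infant under observation?** Each candidate, for an infant withdrawn by the investigator for caregiver non-compliance:

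- Protocol 4.6.2, recovery of information: worded only for withdrawal by the parent or caregiver.
- Protocol 4.6.1, return on Day 29: concerns treatment completion or discontinuation, not study withdrawal.
- Protocol Appendix 1, the column headed Day 29 or early termination: one contact at exit, which cannot capture later events.
- Protocol 5.5.1: follows events already recorded until they resolve or stabilise; it does not look for new ones.
- Protocol 5.3.1: sets the 28-day period without exempting withdrawn patients, but asks at patient contacts, and none is scheduled after withdrawal.
- Protocol 6.2, additional recruitment: depends on the size of the influenza-infected population and on time since symptom onset. A withdrawn infant with a positive PCR still counts in that population, so lost follow-up triggers nothing.
- SAP 1.2.3 against SAP 4.1: the first brings in safety follow-up data from withdrawn patients. The second, read literally, leaves out of the summaries any adverse event recorded after the discontinuation date.

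None of these ensures that new events are sought to Day 29.

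**Size, for illustration.** Inputs from the documents are about 30 patients (Protocol 6.2) and a Cohort III minimum of 3 (Protocol 3.1). The loss rates of 5%, 10% and 20% and the 5% event rate are assumptions. The plan's statement that about 30 patients give a probability above 90% for the PK estimates cannot be reproduced, because no precision target, variance or dropout rate is given. Nothing here depends on it.

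1. *Range left open.* With m infants seen to have a late event and w withdrawn beforehand, the proportion among n dosed lies between m/n and (m + w)/n. For m = 0:
   - n = 30, w = 3: 0% to 3/30 = 10%
   - n = 30, w = 6: 0% to 6/30 = 20%
   - Cohort III, n = 3, w = 1: 0% to 1/3 = 33%

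   The upper ends assume an event in every withdrawn infant.
2. *Expected under-count.* If a fraction d is withdrawn before the window and withdrawal is unrelated to risk, the expected reported incidence is p(1 − d). For p = 5%: 4.75% at d = 5%, 4.5% at d = 10%, and 4.0% at d = 20%. If withdrawn infants are at higher risk, the shortfall is larger.
3. *Chance of seeing a late event at all.* With k infants followed and p = 5%, this is 1 − 0.95^k: 78.5% for k = 30, 75.0% for k = 27, and 70.8% for k = 24.
4. *Chance that a three-infant Cohort III loses at least one.* This is 1 − (1 − d)³: 14.3%, 27.1% and 48.8% at d = 5%, 10% and 20%.

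**PK and virology.** Protocol Appendix 2 places the last PK sample at Visit 4 or 5 (Days 6 to 10). SAP 4.3.2 analyses the visit-based virology endpoints on Days 2, 4, 6 and 10, and the Day 29 swab is conditional. Later withdrawal costs neither. Each infant gives either the Day 2 or the Day 4 sample, so if three neonates were split 2 to 1, one very early loss could leave C24 or C72 without a value in that cohort.

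**The case against.** The rule is permissive: it obliges no one to withdraw anybody. Nothing says that missed diary entries lead to withdrawal, and the SAP handles them as missing data: it counts missing questionnaires and uses only complete assessments in the main time-to-alleviation analysis. The 28-day reporting duty can be read as continuing after withdrawal, an early-termination visit exists, and SAP 1.2.3 expects data from withdrawn patients. The study is descriptive, and the cohort minimums sum to 15 against about 30 planned. All of this stands. It makes the loss possible rather than certain, and probably small.

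Three stronger readings are tempting, and the documents do not support them.

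- A reader might infer that withdrawn infants leave the safety set, so that the exact two-sided 95% upper bound for an unseen event rises from 11.6% (0/30) to 12.8% (0/27), or from 70.8% (0/3) to 84.2% (0/2) in Cohort III. The arithmetic is right, but Protocol 6.1.6 and SAP 3 keep these infants in, so the reported denominators do not change.
- A reader might infer that PK and virology are lost through Day 29. Required PK sampling and the analysed virology visits end by the Day 10 visit.
- A reader might infer that deleting the non-compliance reason would be enough. The investigator's general right to withdraw, and the open-ended list, would remain.

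What the objection does not answer is that no passage requires new events to be sought after an investigator- or Sponsor-initiated withdrawal, and that two SAP passages disagree about summarising such events if they are found.

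**Conclusion.** The point holds as a gap in follow-up. After dosing, withdrawal for caregiver non-compliance ends observation without ending any exposure, and events that start afterwards are counted as absent in an unchanged denominator. The bias in adverse event incidence, if any, is downward and falls mainly on the later onset windows.

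Its size cannot be taken from the documents, because no withdrawal rate is given. At an assumed 10% loss unrelated to risk, a true 5% late-event incidence would be reported as 4.5% on average, and 0/30 seen would leave up to 10% open in the worst case. In a Cohort III of three, one loss leaves up to a third open. No sample-size figure in the plan is shown to be wrong. This is an inexpensive improvement worth making, not a flaw that undermines the study.

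**What to change.** 1. In Protocol 4.6.2, state that once an infant has been dosed, caregiver non-compliance ends at most the affected diary or procedure, and that what is missed is recorded as missing data or as a protocol deviation.
2. In the same section, state that adverse event and concomitant medication follow-up continues to Day 29, by telephone if needed, unless consent is withdrawn.
3. Extend the instruction on obtaining information to withdrawals initiated by the investigator or Sponsor.
4. In SAP 4.1, provide that adverse events collected to Day 29 after withdrawal are included in the summaries, consistent with SAP 1.2.3.

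The cost is wording in two documents and a few calls. The downside is that more infants with partly missing diaries stay in the data set; the SAP's existing rules for incomplete assessments already apply to them. No dosing or treatment rule changes.
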